8.1 Selection

Before carrying out any specific study procedure, informed consent must be obtained, approved by the CEIC, dated and signed. All hematological and biochemical tests, pregnancy tests and carcinoembryonic antigen (CEA) will be analyzed in a local laboratory. Procedures that are part of routine treatment are not considered study specific procedures. Procedures that are part of regular attendance can be used as screening procedures to determine eligibility. Before starting study treatment, all subjects will be evaluated for eligibility. The selection process begins the day the subject signs the informed consent approved by the CEIC and continues until the inclusion of the patient in the trial and subsequent initiation of the study treatment. In this study, only eligible subjects will receive the study treatment.

Before carrying out the study procedures listed below, the KRAS status must be determined by the Central Laboratory of the Navarra University Clinic (CUN) (If the patient already has a prior determination of the status of the KRAS gene, it may be included in the test without the need to re-determine K-RAS).

All subjects must have completed the following procedures in \leq 28 days (unless otherwise specified) prior to the start of study treatment:

Review of the inclusion and exclusion criteria.

Clinical and medication history

The paraffin-embedded tumor block from both the primary site and the liver metastases must be extracted, prepared and sent to the central laboratory (Clínica Universitaria de Navarra, Pathological Anatomy Service) and the blood samples must be extracted, prepared and sent to the central laboratory (Hospital Clinic de Barcelona, Pathological Anatomy Service).

These samples will be used to assess KRAS and BRAF mutational status and expression of PTEN, PIK3, MMP-7, IGFRp, IGF-1, IGFBP-3/5, in addition to other possible biomarkers. KRAS mutation status should be performed by an experienced laboratory using a validated method prior to patient enrollment.

Measurements of resting pulse, blood pressure, respiratory rate and temperature.

Weight and height.

Informed consent.

ECOG (Eastern Cooperative Oncology Group) performance status (\leq 7 days before starting study treatment).

Physical examination, laboratory tests (\leq 7 days before the start of study treatment unless otherwise indicated):

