8.3 Treatment phase

When all eligibility criteria are met, study treatment should be started as soon as possible. Study day 1 is defined as the day the first dose of treatment is received. One cycle is considered every 14 (± 3) day period plus the time it takes for chemotherapy-related toxicities to resolve.

Cetuximab will be administered at a dose of 500 mg / m² every 2 weeks on day 1 of each cycle. The concomitant chemotherapeutic agents used should not be administered until one hour after the completion of the cetuximab infusion.

Subjects with unacceptable FOLFOX6 (m) / FOLFIRI (m) -related toxicities may discontinue FOLFOX6 (m) / FOLFIRI (m) treatment and receive biweekly cetuximab as monotherapy. The combined treatment phase runs from enrollment to the decision to discontinue the administration of FOLFOX6 (m) / FOLFIRI (m). The overall treatment period ends when it is decided to discontinue biweekly cetuximab. Evaluations of subjects receiving biweekly cetuximab as monotherapy will be the same as those expected for combination therapy.

During the time of chemotherapy treatment, the following procedures will be performed:

Record of concomitant medication (day 1 of each cycle).

Adverse event log: including toxicities related to skin or nails (day 1 of each cycle).

ECOG (Eastern Cooperative Oncology Group) performance status (day 1 of each cycle).

Physical examination (day 1 of each cycle).

Measurements of resting pulse, respiratory rate, temperature and blood pressure (day 1 of each cycle).

Weight (day 1 of each cycle).

Body Surface Area (SC): will be calculated on Day 1 of Cycle 1 and at the beginning of any cycle during which the subject's weight has changed by 10% from baseline (ie Cycle 1).

Laboratory tests (≤ 48 hours before the start of each cycle). When possible, the same local laboratory should be used throughout the study:

Hematological tests: hemoglobin, hematocrit, red cell count, mean corpuscular volume, platelets, leukocyte count and differential (neutrophils, lymphocytes, monocytes, eosinophils, basophils).

Biochemical tests: sodium, potassium, chloride, bicarbonate, BUN or urea (depending on local institution practice), LDH, magnesium, creatinine, albumin, total protein, total bilirubin, alkaline phosphatase, ALT, AST, calcium, phosphorus and uric acid.

Serum CEA (every 8 weeks +/- 1 week).

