10.2. Study variables, subgroups and covariates

10.2.1 Principal endpoint

The primary endpoint is progression-free survival comparing two cohorts, which will be defined according to the classification based on the predictive ability of biomarkers to respond.

Progression-free survival time (PFS): time from the date of inclusion to the date of radiological progression or death (whichever occurs first). Subjects who have not exhibited progression while in the study and have not died while in the study will be censored on the last radiological evaluation date with no evidence of progression. Subjects who have completed study treatment before 48 weeks for any reason should be followed up every 12 weeks as described in this protocol. Subjects who have undergone surgery for metastases will not be censored on the date of surgery, but will be followed as described in the study every 12 weeks until progression is documented. Subjects receiving second-line treatment without documented disease progression will be censored on the date of the last radiological evaluation without progression prior to the change in treatment. If for any reason only the baseline CT was performed (resignation of the subject to continue in the study or loss of follow-up), the case will be censored on day +1 of the inclusion date.

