10.2.2 Secondary endpoints

Objective response rate (ORR): incidence of a CR or PR according to the revised RECIST 1.1 criteria.

Duration of response (RD): (calculated only for subjects having an objective response) time from first objective response to progression of radiological disease according to the revised RECIST 1.1 criteria. For subjects who present a response and have not had progression, the duration of the response will be censored on the last assessment date of the evaluable disease.

Overall survival (OS): Time elapsed from the date of inclusion to the date of death. For subjects who have not died or who have been lost to follow-up by the data analysis cut-off date, the SG will be censored on the date of the last contact.

Safety: Type, frequency, intensity of adverse events related to the combination treatment.

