6.5 STATISTICAL METHODS PLANNED IN THE PROTOCOL & DETERMINATION OF SAMPLE SIZE

6.5.1 STATISTICAL AND ANALYTICAL PLANS

6.5.1.1. Primary endpoint

To quantify if the biomarkers BRAF, IGF-1RP/MMP-7 (DP), DP and PIK3CA-PTEN improve the prediction of 12-months progression-free survival (PFS) over the use of just clinical variables in the study population we compared the area under the curve (AUC) of a ROC curve using scores composed by clinical variables with the AUC of scores with the clinical variables plus each of the biomarkers.

PFS was defined as the time from the signature of the ICF date to the radiological progression date or death (whatever occurs first). Subjects who had not shown PD and had not died at database closing were censored on the last date of radiological assessment. Subjects who had concluded study treatment before 48 weeks, due to any cause, underwent follow-up every 12 weeks as described in the protocol. Subjects who had undergone metastatic surgery were not censored on the surgery date but were followed up every 12 weeks until progression was documented. Subjects who received other treatment schemas maintaining the same strategy (chemotherapy + monoclonal antibody) without documented PD, were not censored at the time of the change of treatment. Progression to first line for these patients was considered when applicable according RECIST, independently of treatment received. If by any cause, the baseline CT scan was the only imaging evaluation performed (e.g., subject refusal to stay in the study or lost to follow-up), the case was censored on the inclusion date +1 day.

Two groups with a higher and lower likelihood for tumor progression until 12 months were determined based on the designated classification of clinical variables and following proposed biomarker categories :

1. wt-BRAF vs mutant BRAF

2. wtPI3K and PTEN >3 vs mutant PI3K or PTEN ≤3
3. Non-DP vs DP

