6.5.1.2. Secondary endpoints

- Serum and tumor tissue secondary biomarkers evaluated to predict acquired chemo-resistance including BRAF and PI3K.
- ORR was defined as the incidence of a complete or partial response according to the revised RECIST 1.1 criteria.
- DoR (calculated only for the subjects who present an Overall Response): Time from the first assessment of Overall Response to radiologically-confirmed PD according to the revised RECIST 1.1 criteria. For subjects who showed response and did not show progression, DoR was censored on the last date of assessable disease evaluation reported in the eCRF of the study.
- OS: Time from the signature of the ICF date to date of death. For subjects who did not die or were lost to follow-up on the closing date for data analysis, OS was censored on the date of last contact.
- Safety: Type, frequency, and intensity of AEs related to the combination treatment.

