6.5.1.3. Analysis population

Efficacy variables were analysed in all subjects who provided their informed consents, were included in the trial and did not present significant protocol deviations throughout the study period.

An intention-to-treat analysis in all patient enrolled into the study was not performed because the primary study objective was to evaluate the predictive value of the three biomarker BRAF, IGF-1RP/MMP-7 (Double-positive Phenotype/DP) and PI3K-PTEN on PFS in wt-RAS CRC patients receiving standard chemotherapy plus bi-weekly cetuximab as first-line therapy, but patients with significant protocol deviations (e.g. RAS mutations, missing biomarker data and those not receiving cetuximab treatment) could not contribute to the investigation of the primary objective.

All patients who received study medication were included in the safety analysis. .

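### The SAP starts the PFS and OS clock at consent instead of the protocol's inclusion date, without a stated reason, and so lengthens both by event-free selection time

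*SAP*

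**What the plan says.** Protocol section 10.2.1 defines the primary endpoint thus: "Progression-free survival time (PFS): time from the date of inclusion to the date of radiological progression or death". Section 10.2.2 does the same for survival: "Overall survival (OS): Time elapsed from the date of inclusion to the date of death".

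SAP section 6.5.1.1 reads: "PFS was defined as the time from the signature of the ICF date to the radiological progression date or death". Section 6.5.1.2 reads: "OS: Time from the signature of the ICF date to date of death". The SAP's study description, synopsis and section 6.5.1.5 also use consent. No reason is given, although the heading of section 6.5 presents the methods as those the protocol planned. In 6.5.1.1 a patient with only a baseline CT is still censored one day after inclusion, as in the protocol.

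The dates involved are distinct:

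- Selection starts on the day of consent and lasts until inclusion (protocol 8.1). Enrolment follows confirmation of eligibility (8.2).
- On dosing, protocol 8.3 says: "Study day 1 is defined as the day the first dose of treatment is received".
- Consent must precede the sending of any sample (study scheme note g; section 11.4). For patients without an earlier KRAS result, section 8.1 adds: "Before carrying out the study procedures listed below, the KRAS status must be determined by the Central Laboratory".
- Protocol 8.1 and SAP Table 2 both list consent among the procedures done within 28 days before treatment.
- SAP 6.5.1.3 names, among the deviations that remove a patient from the efficacy set, "missing biomarker data and those not receiving cetuximab treatment".

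**The concern.** To be included, a patient must survive selection and remain eligible. To be in the efficacy set, the patient must also have received cetuximab. No counted death or progression can therefore fall between consent and inclusion. A clock that starts at consent adds this stretch to every patient's PFS and OS, and its length reflects sample logistics and site practice, not disease.

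A lag common to all patients would leave the ranking in a Cox model unchanged. The SAP's primary analysis, however, uses a yes/no status at 12 months (6.5.1.5) on a grid of 12-weekly scans. A fixed cut on a grid is sensitive to where the clock starts. If the lag pushes the week-48 scan past 12 months, a progression found at that scan is recorded as progression-free at 12 months.

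**Working it through.** The plan gives no figure for the lag or its effect, so there is none of its own to reproduce here.

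**Inputs from the documents.** 12-month PFS of 50% and 30% (SAP 6.5.2). Scans every 12 ± 1 weeks (SAP Table 2 footnotes), so week 48 is day 336, window 329 to 343. Screening window of 28 days.

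**Assumptions.** Exponential PFS. The lag L, shown over a range. Scans counted from Day 1, each with its one-week window around the planned date. Steps 3 to 5 take inclusion as close to Day 1, so L there is consent to first dose.

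**Step 1: survival times.** Each PFS or OS time grows by the patient's own lag. With a common lag the medians grow by L: 14/30.44 = 0.46 months, or 28/30.44 = 0.92 months.

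**Step 2: 12-month PFS, progression treated as seen when it occurs.** With S(t) = p^(t/365.25) from inclusion, the consent clock reads S(365.25 − L).

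| L (days) | Exponent | p = 50% becomes | p = 30% becomes |
|---|---|---|---|
| 14 | 351.25/365.25 = 0.9617 | 51.3% | 31.4% |
| 28 | 337.25/365.25 = 0.9233 | 52.7% | 32.9% |
| 42 | 323.25/365.25 = 0.8850 | 54.1% | 34.5% |

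**Step 3: when the week-48 scan crosses 12 months.** For an on-time scan, 365.25 − 336 = 29.25, so the lag must exceed about 29 days. For a scan one week late, 365.25 − 343 = 22.25, so it must exceed about 22 days. At L = 28 the on-time scan is on day 336 + 28 = 364 (before the cut) and the late one on day 343 + 28 = 371 (after it). Counted from first dose the latest is day 343, so none crosses. Counted from inclusion none crosses either, provided dosing follows within about 22 days.

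**Step 4: share of scans that cross.** Let L be uniform on 0 to 28 and the scan offset J uniform on −7 to +7. Crossing needs L + J > 29.25, and the maximum is 35. The probability is (35 − 29.25)²/2 ÷ (28 × 14) = 16.5/392 = 4.2%.

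**Step 5: net change in 12-month status.** Only progressions first seen at week 48 are affected. Between weeks 36 and 48, S(252) − S(336) is 9.1% for p = 50% and 10.5% for p = 30%. The products are 0.042 × 9.1 = 0.38 and 0.042 × 10.5 = 0.44 points. A simulation of the scan calendar gave 52.85% to 53.26% and 32.99% to 33.46%, that is +0.41 and +0.47 points. On 181 patients, 0.005 × 181 = 0.9, less than one patient.

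**Step 6: other lags, same simulation.**

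| Lag | Week-48 scans crossing | Change, 50% / 30% group (points) |
|---|---|---|
| 21 days or less | 0% | 0 / 0 |
| Uniform 14–28 | 8.4% | +0.8 / +0.9 |
| Uniform 0–42 | 30% | +2.8 / +3.3 |
| All at 28 | 41% | +3.9 / +4.5 |

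If the one-week window accumulates from scan to scan, the thresholds in step 3 loosen, and a lag uniform over 0–28 gives 9.6% crossing and +0.9 / +1.0 points. Step 2 and steps 3 to 5 are alternative ways of measuring the effect and must not be added.

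**The case against.** Several counter-arguments reduce the size of the effect, and most of them stand.

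- **The 28-day window.** Consent is on the 28-day list, so a compliant on-time week-48 scan falls by day 364, before the cut. This stands, with one reservation: section 8.1 also places central KRAS testing ahead of those procedures, which could lengthen the lag.
- **The scan anchor.** Protocol 5.1 and the SAP Table 2 imaging footnote speak of a baseline scan and then every 12 weeks. Counting from the baseline CT makes crossing rarer than shown above. This stands.
- **Reclassification.** A reader might infer that 9 to 11% of patients are misclassified. That is everyone progressing between weeks 36 and 48; only those whose scan also crosses the cut change class.
- **The AUC comparison.** The SAP's AUCs with a biomarker differ from the clinical score's by only 0.01 to 0.02, so a reader might infer that the shift could decide the comparison. No AUC effect has been calculated, and points of PFS are not points of AUC. All four scores face the same outcome. Bias between them would need a lag related to BRAF, PI3K/PTEN or DP status, and the documents show none.
- **Prior KRAS results.** A reader might infer that patients needing central testing wait longer by rule. No turnaround rule exists, and the SAP sends every block to the central laboratory at selection and requires RAS confirmation before inclusion.
- **The baseline-only rule.** Inclusion plus one day is a censoring date, not a second time origin, and 12-month status is unknown for these patients on either clock. The rule shows only that the SAP treats inclusion as a separate date.

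One argument fails. Protocol 6.3 loosely ties selection to the moment of signing, which might suggest that consent and inclusion coincide. Sections 8.1 and 8.2 show otherwise.

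**Conclusion.** The discrepancy is certain and unexplained: the SAP's time zero for PFS and OS precedes the protocol's. Its direction is also certain, because the added time cannot contain a counted event. PFS, OS and 12-month PFS are all longer than under the protocol's definition whenever the lag is above zero.

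The size is uncertain because the lag is not reported. For lags spread over the 28-day window, the scan-based effect on 12-month PFS is under one point, or about one point if scan delays accumulate. It reaches several points only if most lags are near 28 days or many exceed it. These figures rest on exponential PFS, the assumed lag distributions and scans counted from Day 1.

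The documents do not support the stronger claim that the biomarker comparison is biased. This should be fixed, because the definition departs from the protocol and favours longer times, but nothing here shows that the primary conclusion depends on it.

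**What to change.** In SAP 6.5.1.1, 6.5.1.2, 6.5.1.5 and the synopsis, restore the protocol's date of inclusion as the single origin for PFS, OS, 12-month status and censoring. If an approved amendment moved the origin, cite it and give the reason.

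Report the consent-to-inclusion and consent-to-first-dose lags, overall and by BRAF, PI3K/PTEN and DP group. Give the consent-based version only as a sensitivity analysis, together with one from first dose. Inclusion and first dose are not interchangeable: because untreated patients are excluded, some event-free time remains between them even on the inclusion clock.

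The cost is a change of wording, a re-run and slightly shorter reported PFS and OS. Inclusion dates must come from the registration records (protocol 6.4), because the SAP's source-verification list (Table 3) names the consent and treatment start dates but no inclusion date.

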5. EXPERIMENTAL PLAN

5.1 Study Design

Single-arm, multicenter, and prospective phase II clinical trial for validation of biomarkers in patients with advanced and / or metastatic colorectal cancer with non-mutated KRAS gene treated with chemotherapy plus biweekly cetuximab as first-line therapy. Patients with non-mutated CCRAyM and KRAS will be eligible.

Patients will be recruited over a 24-month period.

Before inclusion in the study and to confirm eligibility, the investigator or designee will send a sample of the primary tumor to the CUN, which will centrally review the status of KRAS (if the patient already has a prior determination of the status of the KRAS gene, it can be included in the assay without the need to re-determine K-RAS). At the same time, the investigator or designee will review existing radiological images in addition to any other relevant clinical documents (reports, notes, etc.) to confirm that the subject has previously untreated advanced and / or metastatic colorectal cancer.

The proposed biomarkers will be measured at the beginning of the study. Investigators can treat patients with CCRAyM and non-mutated KRAS with biweekly FOLFOX6 (m) or FOLFIRI (m) + cetuximab. Other investigative agents will be excluded.

FOLFIRI (m) / FOLFOX6 (m) will be administered once every 2 weeks until 6 months of treatment, disease progression (PE), or unacceptable toxicity. Cetuximab will be administered every 2 weeks as stipulated in this protocol until disease progression. If patients do not show progression after 6 months of treatment with FOLFIRI (m) and FOLFOX6 (m), they will continue to receive biweekly cetuximab as monotherapy until progression.

Subjects who stop receiving FOLFOX6 (m) / FOLFIRI (m), for example due to toxicity, may receive biweekly cetuximab as monotherapy until disease progression. Following discontinuation of biweekly cetuximab, the treatment period will end and subjects will attend a follow-up safety visit 30 ± 3 days later.

Throughout the trial, subjects will be assessed for tumor response using Response Assessment Criteria for Solid Tumors (RECIST 1.1). The tumor response of the subjects will be evaluated by CT (helical or conventional) thoracic and abdominal performed in the baseline phase and every 12 weeks (three months) until the progression of the disease. In subjects with symptoms that indicate disease progression, tumor response should be assessed at the time of symptoms.

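### The day +1 censoring rule for patients with only a baseline CT makes no exception for death, so it contradicts the definition of death as a PFS event

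*SAP*

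**What the plan says.** SAP 6.5.1.1 defines PFS as "the time from the signature of the ICF date to the radiological progression date or death (whatever occurs first". Protocol 10.2.1 has the same event definition, counted from inclusion. The general censoring rule in SAP 6.5.1.1 covers only patients without an event: "Subjects who had not shown PD and had not died at database closing were censored on the last date of radiological assessment". SAP 6.5.1.5 again restricts censoring to patients with neither progression nor death, and Protocol 10.2.1 has an equivalent sentence.

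A special rule follows. The SAP states: "If by any cause, the baseline CT scan was the only imaging evaluation performed", then "the case was censored on the inclusion date +1 day". The Protocol opens its version with "If for any reason only the baseline CT was performed" and uses the same date. Each gives refusal to continue and loss to follow-up in a parenthesis. The SAP marks these as examples; the Protocol does not. Neither mentions death.

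Protocol 5.1 has CT "performed in the baseline phase and every 12 weeks (three months) until the progression of the disease", so the first scheduled post-baseline scan is at week 12.

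**The concern.** A patient who dies before a second scan meets the trigger of the special rule exactly, and also meets the definition of a PFS event. One rule gives an event on the date of death; the other gives censoring at day 1. Two programmers could derive different primary endpoints from the same text.

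The patients at stake include the earliest failures in the trial. The case is foreseeable: Protocol 6.1 admits ECOG 2 and a life expectancy of three months or more, about the time of the first scan, and SAP 6.5.1.5 provides for patients with no second CT when it defines who is assessable for response. The biomarker groups are small. SAP Table 6 has 20 BRAF-mutant and 23 double-positive patients, so one patient is 1/20 = 5% of the mutant group. The AUCs in the SAP synopsis run from 0.66 to 0.69 against 0.67 for the clinical score, so the differences under study are only 0.01 to 0.02.

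**Working it through.** **1. The rules applied to one patient.** Take, for illustration, a death at week 8 with no scan after baseline.
- PFS definition (both documents): event at week 8.
- General censoring rule (SAP 6.5.1.1 and 6.5.1.5, Protocol 10.2.1): not censored, because the patient has died.
- Day +1 rule (both documents): censored at inclusion +1 day.

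No text ranks the rules. SAP 6.5.1.5 refers to Section 7.5.1.1 for details of censoring, but the text stands in 6.5.1.1 and contains both rules.

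**2. Who is caught.** The trigger is the absence of any later scan, not death before week 12 as such. Symptoms suggesting progression call for assessment at that time (Protocol 5.1, tumour response section), and patients stopping treatment for reasons other than progression are imaged at the safety visit (Protocol 8.4). Either scan takes the patient outside the rule. Conversely, the literal rule also catches a later death in a patient who was never rescanned.

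**3. The plan's event target.** Protocol 10.2.5 gives 115 events for 60% vs 40% PFS at 12 months, two-sided 5%, 80% power and a 40/60 split.
- HR = ln 0.4 / ln 0.6 = 1.794; k = 60/40 = 1.5.
- Freedman: (1.960 + 0.842)² × (1 + 1.5 × 1.794)² / [1.5 × (1 − 1.794)²] gives 114 after rounding up, against 115 stated.

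The target itself does not depend on the censoring rule. If 4, 9 or 18 events (2%, 5% or 10% of the 181 efficacy patients) were missing from a fixed pool of 115, the Schoenfeld power Φ(√(0.24d) × ln HR − 1.96) at the SAP's stated HR of 1.79 would go from 86.4% to 85.2%, 83.6% or 80.2%. This counts lost events only; the bias below is separate.

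**4. Bias in 12-month PFS.** Let S be the true 12-month PFS and f the fraction who die unscanned before 12 months. Of n patients, nS are progression-free at 12 months. Day-1 censoring takes nf certain failures out of the risk set before other events occur, so the estimate becomes nS/(n − nf) = S/(1 − f), ignoring other early censoring. The values of f are assumptions; S is taken from SAP 6.5.2.

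| f (assumed) | Deaths in 181 | True 50% becomes | True 30% becomes |
|---|---|---|---|
| 2% | about 4 | 51.0% | 30.6% |
| 5% | about 9 | 52.6% | 31.6% |
| 10% | about 18 | 55.6% | 33.3% |

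**5. Bias in the contrast.** The same formula is applied to each group, with HR = ln(poor) / ln(good) under exponential PFS. The true values are 50% vs 30%: gap 20 points, HR 1.74.

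| f good / f poor (assumed) | PFS good vs poor | Gap (points) | HR |
|---|---|---|---|
| 5% / 5% | 52.6% vs 31.6% | 21.1 | 1.80 |
| 2% / 5% | 51.0% vs 31.6% | 19.4 | 1.71 |
| 5% / 10% | 52.6% vs 33.3% | 19.3 | 1.71 |
| 2% / 10% | 51.0% vs 33.3% | 17.7 | 1.63 |

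With equal rates the contrast widens slightly. It shrinks in the scenarios where the poor group has the higher rate.

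**6. The 12-month ROC analysis.** SAP 6.5.1.5 uses logistic regression for 12-month PFS but does not say how patients censored before 12 months enter it. If day-1 censored deaths are dropped, the observed proportion is again S/(1 − f). If they are coded as not progressed, it is S + f: for S = 50%, 52%, 55% or 60% at f = 2%, 5% or 10%.

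**The case against.** The strongest reply is that the day +1 rule was never meant for deaths. Both documents name death as an event, and the general rules censor only event-free patients. Those rules leave one gap: a living patient with no post-baseline scan has no last assessment date after baseline. The day +1 sentence fills that gap, and its illustrations are refusal and loss to follow-up. In the Protocol the parenthesis can even be read as limiting. This is a plausible account of the intent, and it means that the documents do not show that any death was in fact censored. It does not remove the conflict: the trigger covers any cause, the SAP's illustrations are marked as examples, and the sentence is the more specific rule.

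A reader might go further and infer three things that the documents do not support.
- That clinical progressions are removed as well. PFS counts radiological progression or death, so an unscanned clinical progression was never an event. The rule only sets that patient's censoring date, and an event is lost only if the patient later dies.
- That everyone who dies before week 12 is affected. Symptom-triggered and safety-visit scans exclude some of them.
- That a particular loss of power or hazard ratio for BRAF follows. Such figures need assumed death rates and a Cox contrast of 161 vs 20 patients. The 50% vs 30% assumption belongs to the two-group classification, and the SAP's primary analysis compares AUCs. No effect on AUC has been calculated here.

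**Conclusion.** The point holds as an unresolved contradiction in the primary endpoint. Followed as written, the day +1 rule censors deaths without a post-baseline scan, and for deaths within 12 months that censoring is informative. The consistent effect is an overstated 12-month PFS: by 0.6 to 5.6 points across true values of 30% and 50% and an assumed f of 2% to 10%. Dilution of the biomarker contrast depends on clustering. In the most unequal case shown (2% vs 10%), the gap falls from 20 to 17.7 points and the HR from 1.74 to 1.63; with equal 5% rates neither falls. The documents report no count of unscanned deaths, overall or by biomarker group, so all these sizes are conditional on assumed rates. That these deaths cluster in a poor-prognosis group is possible but not documented. The rule appears in both the Protocol and the SAP, so it is not a late change made by the SAP.

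**What to change.** Reword the rule in SAP 6.5.1.1, and align Protocol 10.2.1, as follows:
- Day +1 censoring applies only to patients who are alive, have no documented progression and have no post-baseline tumour assessment.
- Death without a post-baseline scan is a PFS event on the date of death.
- Such a death within 12 months counts as a failure in the logistic and ROC analysis. State also how patients censored before 12 months are handled there.
- Report the number of deaths without a post-baseline scan, overall and by biomarker group. Add a sensitivity analysis under the literal rule if the number is not zero.

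In the same edit, settle the time origin (the SAP clock starts at consent signature but the censoring date counts from inclusion) and correct the cross-reference to Section 7.5.1.1.

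The cost is a few sentences and one count. The date of death is already in the source-data verification list (SAP Table 3), so no new data are needed. The SAP already reports AUCs, so check how these deaths were derived and rerun the scores only if any was censored at day 1.
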